17. SUBJECT CONFIDENTIALITY

At all times throughout this study, all parties shall strictly observe the confidentiality of subject's health information. All data shall be secured against unauthorized access. Each subject participating in this study will have consented to allow access to her data, as described during the informed consent process and documented in the signed informed consent form. Each subject will also sign an Authorization For Release of Protected Health Information (PHI) form granting ContraMed and its designees access to her medical records, should she receive medical care from non-study sites where she gets care (e.g., emergency room, urgent care, etc.). Each subject will be assigned a unique identifier. All eCRFs will be tracked, evaluated, and stored using only this unique identifier. HIPAA guidelines and regulations will be followed.

The Investigator will maintain a confidential study subject list identifying all enrolled subjects. This list will contain the assigned study subject's unique identifier and name. The Investigator bears responsibility for keeping this list confidential. This list will not be provided to the study Sponsor and is only to be used at the study center.

Monitors and auditors will have access to the study subject list and other personally identifying information of study subjects to ensure that data reported in the eCRFs corresponds to the person who signed the consent form and the information contained in the original source documents. Such personal identifying information may include, but not limited to, the subject's name, address, date of birth, gender, race and medical record number.

In an effort to protect subject confidentiality, any source documents copied for monitoring purposes by the Sponsor or designee will be identified using the subject's assigned unique identifier and personal identifying data will be obscured.

18. PREGNANCY DETERMINATION AND FOLLOW UP

Suspected pregnancy will be confirmed with a urine pregnancy test. A positive urine test will be confirmed by a serum test. Pregnancies will be promptly

confirmed and dated by ultrasound evaluation and medical assessment as needed. Presence or absence of the study device will also be determined by ultrasound. Removal of the study device, if in place, will be performed as deemed appropriate by the study physician and upon obtaining subject consent (note: removal itself may be performed by another clinician, such as a nurse practitioner). Consideration of study device removal should include the following standard of care criteria: If the subject has an intrauterine pregnancy in the first trimester and the study device is seen to be in the uterine cavity or cervix on ultrasound, remove the study device if the retrieval threads are visible. If the retrieval threads are not accessible, the IUD should remain in the uterus until delivery (abortion or term).

Subjects will be counseled and followed through completion of pregnancy, and the clinical outcome will be recorded.

19. DATA MONITORING AND QUALITY CONTROL

19.1 Monitoring of Clinical Sites and Investigators

Periodic monitoring visits will be made at the investigational site throughout the clinical study to ensure that the Investigator obligations are fulfilled and all applicable regulations and guidelines are being followed. These visits will ensure that the facilities remain acceptable, the investigational plan is being followed, the IRB and local authorities have been notified of approved investigational plan changes as required, complete records are being maintained, appropriate and timely reports have been made to the Sponsor and/or its designees and the IRB, study device and study device inventory are controlled and the Investigator is carrying out all agreed upon activities. The Sponsor will reserve the right to remove either the Investigator or the investigational site from the study for noncompliance with the investigational plan or regulations. See monitoring plan for full details.

19.2 Electronic Case Report Forms (eCRF)

Electronic case report forms (eCRFs) will be used to collect all subject data during the study

The Investigator is responsible for the accuracy and completeness of all data on the eCRFs.

Sponsor personnel or designee will review completed eCRFs at regular intervals throughout the study. Information on the eCRFs will be compared to information originally recorded on source documents related to the study. Information on the eCRF must match the same information on the source documents or a data query will be issued.

The Sponsor will use the study data for statistical and tracking purposes and will treat the information as confidential.

19.3 Data Collection and Management

Qualified study staff at the investigational site will perform primary data collection. The Sponsor monitors and/or designees will perform clinical study monitoring of 100% of the subjects who pass screening evaluations and undergo VeraCept placement. This monitoring will include review of eCRF data with verification to the source documentation.

All eCRFs will be reviewed for completeness, validity, and consistency. Queries will be generated and resolved with the sites and all protocol deviations will be recorded on the eCRF.

19.4 Maintaining Records

The Sponsor and/or its designees will maintain copies of correspondence, data, shipment of study devices, adverse study device effects and other records related to the clinical study. The Sponsor will maintain records related to the signed Investigator agreements.

19.5 Record Retention

All study records and reports will remain on file for a minimum of two years (or longer if local law or clinic administration requires) after the latter of the following two dates: 2 years after a marketing application is approved, or if an application is not approved, until 2 years after shipment and delivery of the study device for investigational use is discontinued and FDA has been so notified. Study records should only be discarded upon written notification from the Sponsor. All records and reports are subject to inspection at any time.

19.6 Investigational Product Accountability

The Sponsor or designee shall ship investigational study devices only to qualified investigators. The Investigator shall maintain adequate records of the receipt and disposition of all investigational study devices. The Investigator shall return any unused devices, opened or unopened, to the Sponsor or its designees when the study has completed.

19.7 Study Closeout

Upon completion of the clinical study (when all subjects enrolled have completed the last required visit and the eCRFs and queries have been completed), the Sponsor and/or its designees will notify all investigational sites of closeout. Unused study devices, and any unused study materials will be collected and returned to the Sponsor and/or its designees.

19.8 Audits And Inspections

The Investigator will permit access to original medical records and provide all requested information in the event that the Sponsor and/or its designees or national regulatory authorities initiate any audits or inspections. In the case that it is a non-Sponsor initiated audit, the investigator must contact the Sponsor as soon as possible after notification of intent to audit.

19.9 Annual, Interim And Final Report

Annual, interim and final reports will be completed in accordance with the applicable local and federal regulations. A final report will be completed even if the study is prematurely terminated.

20. STATISTICAL METHODOLOGY AND ANALYSIS

A detailed statistical analysis plan will be finalized prior to locking the database to conduct the statistical analysis in accordance with the methods presented below.

20.1 Analysis Populations

The following analysis populations will be created:

All Enrolled: All subjects enrolled into the study.

Intent to Treat (ITT) / Safety: All enrolled subjects who underwent the study device placement procedure, regardless of whether the study device was successfully placed or not.

Evaluable for Pregnancy (EP):

Subjects must meet requirements 1 and 2 to be EP. Subjects must also meet either requirement 3 **or** requirement 4 to be EP.

- 1. between 18 to 35 years of age (inclusive) at enrollment
- 2. at least one report of pregnancy status after being enrolled AND
- have at least 1 cycle of diary with intercourse and without any backup contraception or emergency contraception (EC) OR
- 4. became pregnant while VeraCept was in place.

Evaluable for Cycle Control (ECYC): all subjects Evaluable for Pregnancy with at least one cycle for which: A) a pregnancy did not occur; and B) there is bleeding related diary data.

20.2 Disposition Of Subjects

The number of subjects who are enrolled, complete scheduled study visits and who complete the study will be summarized for the All Enrolled population.

20.3 Demographic And Other Subject Characteristics

Subject demographics and pre-treatment characteristics will be summarized for the All Enrolled Population.

20.4 Extent Of Exposure

Exposure (number of subjects with VeraCept placed and number of cycles of use) to the study device will be summarized.

20.5 Pre-Trial And Concomitant Medications

Concomitant medications include any medication or health product (any prescription medications or over-the-counter preparations) taken during the

study. Pre-trial medications include any routine medications taken within 30 days of enrollment. The number and percentage of subjects using medications, as captured on the Concomitant Medication eCRF, will be tabulated according to the medication's World Health Organization Anatomical Therapeutic Drug Class and Generic Term. Pre-trial and concomitant medications will be presented separately.

20.6 Primary Outcome

The primary outcome measure is effectiveness and will be evaluated as absence of pregnancy during VeraCept use for up to 12 months. Pregnancies judged to have occurred while a study device was in place (determined by ultrasound and medical assessments) will be included in the analysis of pregnancies.

For the primary evaluation of effectiveness, the Pearl index (and 95% confidence intervals) will be calculated through 12 months for cycles in subjects aged 18-35 at the time of VeraCept placement, excluding the following (unless the subject became pregnant in the cycle):

- Cycles where back-up contraception use was documented on the daily diary
- Cycles with no intercourse.
- Cycles in which emergency contraception was used

The EP population will be used for the primary evaluation of effectiveness.

Life table analyses will be used as further assessment of pregnancies. Secondarily the Pearl index and life table analyses will be done through 3 years.

20.7 Safety And Other Outcome Measures

All safety and other outcome measures will be analyzed using the ITT/Safety Population unless noted otherwise. Confidence intervals will be provided to support interpretation of the observed safety rates.

VeraCept Characteristics

Study device ease of placement and placement success will be summarized. Cumulative study device expulsion rates will be summarized

Adverse Events

The number and percentage of subjects with each adverse event and serious adverse event will be presented in a table by MedDRA system-organ class and preferred term. Summaries will also be presented by relationship to the VeraCept placement or removal procedure and the severity of the adverse event. All adverse events will be summarized with special attention to those events that may be related to an intrauterine contraceptive, including:

- Anemia
- Back pain
- Dysmenorrhea
- Dyspareunia
- Ectopic pregnancy
- Embedment, which in some cases may require surgical removal

- Expulsion, partial or complete
- Intrauterine pregnancy
- Leukorrhea
- Medical diathermy
- Menstrual flow, prolonged / vaginal bleeding
- Menstrual spotting
- Movement of study device during MRI
- Pain and cramping
- Pelvic infection, which can lead to Fallopian tubal damage leading to ectopic pregnancy or infertility, hysterectomy, sepsis and rarely death
- Pelvic Inflammatory Disease (PID), which can lead to tubal damage leading to ectopic pregnancy or infertility, or infrequently can necessitate hysterectomy, or cause death.
- Uterine perforation, which may lead to pre-operative imaging followed by laparscopy or laparotomy to remove the IUD from the peritoneal cavity
- Septic abortion
- Uticarial allergic skin reaction
- Vaginitis
- Vasovagal reaction at the time of placement, including fainting.

VeraCept Safety-Related Removal Rates and Expulsion Rates

Cumulative VeraCept safety-related removal rates and expulsion rates at each year will be summarized.

Bleeding and Spotting Patterns

Vaginal bleeding and spotting will be recorded daily by the subject in her diary. The ECYC population will be used for the bleeding and spotting summaries. The number of bleeding or spotting days will be summarized for each cycle. In addition, bleeding and spotting will be summarized separately. Subjects who discontinue the study due to bleeding complaints prior to completing one 28-day cycle will be included in the bleeding analysis.

Other Safety Assessments

Changes in vital signs from baseline to each visit will be summarized for the physical examination and vital sign results.

20.8 Monitoring of Safety and Pregnancy

Periodic reviews of safety and pregnancy rates will be conducted by a Medical Monitor. New findings of safety concerns or pregnancies will be communicated to all study sites. A Clinical Events Committee (CEC) will be assembled to review study data if >1 pregnancy is reported.

APPENDIX 1. INVESTIGATOR RESPONSIBILITIES

The Investigator is responsible for ensuring that the clinical study is conducted according to the Investigator Agreement, Clinical Investigational Plan (CIP), all conditions of national regulatory requirements, the governing IRB, and in accordance with the highest standards of medical and ICH E6 Good Clinical Practice (GCP), and the Declaration of Helsinki.

The Investigator(s) shall be responsible for the day-to-day conduct of the investigation as well as for the safety and well-being of the human subjects involved in the clinical investigation. The Investigator(s) shall:

- a) Have the resources to conduct the investigation properly
- b) Ensure that conducting the investigation will not give rise to a conflict of interest
- c) Obtain from the Sponsor the information which the Investigator(s) judges essential about the study device and be familiar with this information
- d) Be well acquainted with the protocol before signing it
- e) Support the monitor and/or auditor, if applicable, in their activities to verify compliance with the protocol, to perform source data verification and to correct the eCRFs where inconsistencies or missing values are identified
- f) Discuss with the Sponsor management any question or modification of the protocol
- g) Make sure that the protocol is followed by all responsible for the conduct of the study at his/her institution. Any deviation shall be documented and reported to the study Sponsor.
- h) Make the necessary arrangements to ensure the proper conduct and completion of the investigation
- i) Make the necessary arrangements for emergency treatment, as needed, to protect the health and welfare of the subject
- j) Ensure that appropriate IRB approvals are obtained prior to the start of the investigation
- k) Provide the communication from the IRB to the study sponsor
- I) Inform the IRB about any serious adverse device effects in accordance with the IRB requirements.
- m) Inform the Sponsor about any adverse events and adverse device effects in a timely manner and in accordance with the timelines laid out in this protocol
- n) Endeavor to ensure an adequate recruitment of subjects
- o) Ensure that the subject has adequate time and information to give informed consent
- Ensure that informed consent authorization to release protected health information is obtained and documented prior to any study specific evaluations or procedures being performed

- q) Ensure that clinical records are clearly marked to indicate that the subject is enrolled in this study
- r) Provide subjects with well-defined procedures for any emergency situation and safeguard the subject's interest
- s) Ensure that information which becomes available as a result of the clinical investigation which may be of importance to the health of a subject and the continuation of the investigation shall be made known to: 1) the Sponsor;
 2) the subject; and 3) the subject's personal clinician (with the subject's approval), if pertinent to the safety or well-being of the subject
- Inform the subject and/or the subject's physician (with the subject's approval) about any premature termination or suspension of the investigation with a rationale for study termination
- Have primary responsibility for the accuracy, legibility and security of all investigational data, documents and subject records both during and after the investigation
- v) Review and sign each subject's eCRFs (last page only)
- w) Be responsible for the supervision and assignment of duties at his/her study center
- x) Ensure that all investigational devices are accounted for (number of devices used, discarded and returned to the Sponsor)
- y) Disclose to the Sponsor sufficient accurate financial information to allow the Investigator to submit complete and accurate certification or disclosure statements, and update the information during the course of the investigation and for one year following the completion of the study
- Ensure that the Investigator discloses to the Sponsor if the Investigator has ever been associated with terminated research and the reason for such termination is provided
- aa) Ensure that the Investigator discloses to the Sponsor if the Investigator has ever been barred from conducting or participating in clinical research.

## **LIST OF ABBREVIATIONS**

F	
AE	Adverse Event
BMI	Body Mass Index
CI	Confidence Interval
CRF	Case Report Form
CSR	Clinical Study Report
EC	Emergency Contraception
ECYC	Evaluable for Cycle Control
EP	Evaluable for Pregnancy
HEENT	Head, Eyes, Ears, Nose and Throat
IND	Investigational New Drug
ITT	Intent-To-Treat
IUD	Intrauterine Device
LTFU	Long Term Follow up
MedDRA	Medical Dictionary for Regulatory Activities
PT	Preferred Term
SAE	Serious Adverse Event
SAP	Statistical Analysis Plan
SD	Standard Deviation
SOC	System Organ Class
WHO	World Health Organization

## 1.0 INTRODUCTION

This statistical analysis plan (SAP) was developed based on the Version 1.00 SAP for Year 1 data analysis, after reviewing the Sebela Pharmaceuticals Development LLC (Sebela) CMDOC-0008 study protocol (Version 5.0, dated as 29SEP2017) and electronic case report forms (eCRFs, dated as 30JAN2018), but before final analysis of the Year 2 and Year 3 data analysis had begun. Detailed information is given to aid in the production of the statistical outputs and the statistical section of Final Clinical Study Report (CSR). This document gives a summary of the protocol and describes the populations that will be analyzed. All subject characteristics and the efficacy and safety parameters that will be evaluated, along with the specific statistical methods, are described.

#### 2.0 PROTOCOL SUMMARY

## 2.1 Background

Of all contraceptive methods, oral contraceptives are used by 30% of sexually active women. The more effective methods, such as intrauterine contraceptives, are used by fewer than 10% of women. The CHOICE Study showed that the pill failure rate is 17-20 times higher than the failure rate with intrauterine devices.

Intrauterine devices have high initial costs, so early discontinuation rates have profound impacts on their cost-effectiveness. The early rates of user dissatisfaction due to complications or side effects may be associated with the materials used in these devices and/or their design. The VeraCept Intrauterine Contraceptive by Sebela is designed as a birth control device with low-dose copper trying to achieve high contraceptive effectiveness, minimal side effects and improved mechanical advantages.

## 2.2 Objectives

The scientific objective of this study is to evaluate the effectiveness, study device placement, safety, and tolerability of the VeraCept Intrauterine Contraceptive as birth control in parous and nulliparous women of child-bearing age.

The purpose of the study is to obtain the safety and effectiveness data necessary to support an Investigational New Drug (IND) application to the U.S. Food and Drug Administration (FDA) for a longer term Phase III pivotal clinical study.

#### 2.3 Trial Design

This is a prospective, multi-center, single-arm, open-label, Phase II clinical study. Each subject will be followed for 12 months after device placement for the protocol endpoints, and then every 6 months thereafter for those subjects who wish to continue study device use up to a maximum of 3 years.

Physical assessment (office visit) will occur at Weeks 6, 13, 26 and 52 after placement, with monthly telephone contact. For those subjects who wish to continue study device use after 12 months (up to 2 additional years for a total maximum of 3 years), follow-up office visits will occur every 6 months, and also contacted by phone calls, e-mail or text

message every 28 days (Cycle Contact). Additional visits will be conducted if necessary for safety issues.

## 2.4 Study Endpoints

## 2.4.1 Primary Endpoints

The primary outcome measure is study device effectiveness, evaluated as the absence of pregnancy up to 12 months (13 cycles of 28 days each) of VeraCept use.

Contraceptive failure rate will be calculated using the Pearl Index through 13 cycles. All evaluable cycles prior to discontinuation or planned removal at 12 months (13 cycles) will be included in the primary analysis of effectiveness. The calculation will be first done for all ("Total") subjects, and then for sub-groups of parous ("Parous") and nulliparous ("Nulliparous") women of child-bearing age.

## 2.4.2 Secondary Endpoints

The secondary endpoints concern the:

#### **Study Device Placement**

- Ease of placement
- Placement success

## **Subject Safety**

- Serious Adverse Events
- Adverse Events

#### **Tolerability**

- Bleeding and spotting patterns
- Discontinuation rate and reasons for discontinuation.

#### 2.5 Sample Size Consideration

No formal sample size calculations were performed for this exploratory study. It is estimated that with 225 subjects enrolled with age 18-35, a 12-month (13 cycles) Pearl Index of 0.6 (1 observed pregnancy), and 2,015 evaluable cycles, we will observe a 95% confidence interval (0.1, 3.3) for the Pearl Index.

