In general, summaries of quantitative variables will include the sample size, mean, median, standard deviation, minimum, and maximum. For qualitative (categorical) variables the summaries will include the number and percentage of subjects in each category.

SAMPLE SIZE

No formal sample size calculations were performed for the study. It is estimated that with 225 subjects enrolled with age 18-35, a 12-month Pearl Index of 0.6 (1 observed pregnancy), and 2,015 evaluable cycles, we will observe a 95% confidence interval for the 12 month Pearl Index of (0.1, 3.3).

2.015 evaluable cycles assumes that in the overall study:

- Each subject will average10 evaluable cycles of VeraCept use
- 1% of subjects will not provide any diary data and will be excluded from the primary efficacy population
- Subjects will not have intercourse or will use backup contraception in 9.2% of cycles

ABBREVIATIONS AND DEFINITIONS OF TERMS

AE	Adverse Event
BMI	Body Mass Index
BP	Blood Pressure
BUN	Blood Urea Nitrogen
BV	Bacterial Vaginosis
C	Celsius
CBC	Complete Blood Count
CCTN	Contraceptive Clinical Trials Network
CFR	Code of Federal Regulations
cm	Centimeters
CRF	Case report forms
Cu	Copper
CVR	Contraceptive vaginal ring
d	Day
DHHS	Department of Health and Human Services
dL	Deciliter Deciliter
DSMB	Data Safety Monitoring Board
EC	Emergency contraception
eCRF	Electronic case report form
EDC	Electronic data capture
ECYC	Evaluable for Cycle Control
EE	Efficacy Evaluable
EMR	Electronic medical records
ENDTX	End of treatment
EP	Evaluable for Pregnancy
F	Fahrenheit
FDA	Food and Drug Administration
FSH	Follicle Stimulating Hormone
	Gram
GCP	Good Clinical Practices
GnRH	Gonadotropin-Releasing Hormone
hCG	Human Chorionic Gonadotropin
HD	Health Decisions
HPV	Human Papillomavirus
ICH	International Conference on Harmonization
IEC	Independent Ethics Committee
IND	Investigational New Drug
IRB	Institutional Review Board
ITT	Intent-To-Treat
IUD	Intrauterine Device
kg	Kilograms
L	Liter
LTFU	Lost to follow up
MedDRA	Medical dictionary for regulatory activities
MITT	Modified Intent To Treat
mg	Milligrams
mL	Milliliter
11115	Minimo

mm	Millimeter
NDA	New Drug Application
NIH	National Institutes of Health
N/A	Not Applicable
OC	Oral Contraceptive(s)
Pap Test	Papanicolaou Test
PD	Pharmacodynamics
PK	Pharmacokinetics
PP	Per-protocol
SAE	Serious Adverse Event
SAP	Statistical Analysis Plan
SAS	Statistical Analysis Software
SCCC	Statistical and Clinical Coordinating Center
SCRN	Screening

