## 3.1.2 Analysis of 1-Year data

An analysis of the 1-year data was performed after all the subjects are enrolled and all the 1-year data were collected, monitored, and cleaned. All outputs in Section 5.2 that involve 1-year data were created since this analysis was the final analysis of the 1-year data. The analysis of 1-year data was the main analysis for the study. Secondarily, an analysis will be done at the end of the study to include all 3-year data.

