## 3.7 Efficacy Analyses

## 3.7.1 Efficacy Analyses for Year 1 Data

Primary efficacy analysis was performed for the first year of the study (through Day 364) for Evaluable for Pregnancy population, by using Pearl Index. Pearl Index is defined as the number of pregnancies in 100 woman-years of method use. Pearl Index was calculated in subjects aged 18-35 at the time of VeraCept placement through the date of VeraCept removal or pregnancy, excluding the following cycles, unless the subject became pregnant in that cycle:

- When back-up contraception use was documented on the daily diary
- When the subject had no intercourse.

The Pearl Index formula is:

$$r = \frac{n}{L} \times 1300 = \frac{\text{Number of pregnancies}}{\text{Number of woman-cycles of pregnancy-risk}} \times 1300$$

where n is the number of pregnancies, and L is the number of woman-cycles, i.e., sum of the number of cycles each woman used the VeraCept up to and including the cycle of conception or until the time of VeraCept removal/expulsion, whichever comes earlier. The cycles of pregnancy-risk will be calculated as (Date of VeraCept removal/expulsion – Date of VeraCept placement + 1) / 28 for women who are not pregnant, and as (Date of pregnancy – Date of VeraCept placement + 1) / 28 for women who became pregnant

during the study. On-treatment pregnancies are defined to be pregnancies for which the estimated date of conception was within 7 days after study device expulsion or removal (the earlier of expulsion and removal dates will be used). The last cycle of pregnancy-risk can be a partial cycle and the partial cycle at risk is determined by dividing the number of days at risk in the cycle by 28 (e.g., 14/28 = 0.5 cycle of risk). If a cycle has a day with no information about backup contraception, that cycle will be excluded from the analysis (unless the subject became pregnant in that cycle).

To get the confidence interval (CI) for the Pearl Index, first the CI for the n (number of pregnancies) will be approximated by Poisson distribution sample mean's CI as

$$(\frac{\chi^{2}(\alpha/2;2n)}{2},\frac{\chi^{2}(1-\alpha/2;2n+2)}{2})$$

where  $\chi^2(\alpha/2;2n)$  in the lower limit is the Chi-square distribution (degrees of freedom = 2n) percentile with lower tail area (probability)  $\alpha/2$ , and  $\chi^2(1-\alpha/2;2n+2)$  in the upper limit is similarly defined. If n = 0, the lower limit will be set as 0.

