Then the 95% CI for Pearl Index will be estimated as follows by set  $\alpha = 0.05$ .

( 
$$\frac{\chi^2(\alpha/2;2n)}{2}$$
 / L x 1300,  $\frac{\chi^2(1-\alpha/2;2n+2)}{2}$  / L x 1300 )

The summary table will present the number of subjects in the EP analysis population, number of pregnancies and the number of cycles of risk in addition to the Pearl Index and its 95% CI, for the following 3 scenarios:

- All EP subjects
- EP subjects with at least one live birth
- EP subjects never had live birth

Life-Table (Kaplan-Meier) method will also be used to present probabilities of pregnancy through 1-year (13 cycles) interval (through Day 364). The Evaluable for Pregnancy population will be used for the analysis and cycles will be compressed to provide contiguous cycles.

All efficacy analyses will be first done for all EP population, and then done by parity for 2 sub-groups of EP population: one sub-group subjects who had live child birth, and the other sub-group subjects who had not.

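### The planned 95% CI of (0.1, 3.3) for one pregnancy in 2,015 cycles does not reproduce; the SAP's own formula gives (0.02, 3.6), and no planning method is named

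*SAP*

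**What the plan says.** SAP 2.5 describes the study as exploratory, with no formal sample size calculation. It gives one precision figure, based on "a 12-month (13 cycles) Pearl Index of 0.6 (1 observed pregnancy), and 2,015 evaluable cycles", and concludes that "we will observe a 95% confidence interval (0.1, 3.3) for the Pearl Index". The Sample Size part of the Protocol synopsis has the same inputs and the same limits: "we will observe a 95% confidence interval for the 12 month Pearl Index of (0.1, 3.3"). Neither place says how the interval was calculated.

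The analysis method is explicit. In SAP 3.7.1, "the CI for the n (number of pregnancies) will be approximated by Poisson distribution", using chi-square percentiles. Both limits are then divided by the number of cycles at risk and multiplied by 1300. SAP 2.4.1 sets the length of the year: "absence of pregnancy up to 12 months (13 cycles of 28 days each").

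**The concern.** A stated interval should follow from its stated inputs. Here the inputs are complete (one event, 2,015 cycles, 13 cycles per year, 95%), and the SAP supplies a formula a few pages later, yet the formula returns different limits. The planning statement could rest on another method, but then the method should be named and its limits should agree with 2,015 cycles.

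This is the only precision statement for the planned size on the primary endpoint. The upper limit is the bound that matters for a contraceptive failure rate, and the printed one is lower than the SAP's method gives.

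**Working it through.** **Inputs.** Pregnancies n = 1, cycles L = 2,015 and 13 cycles per 12 months (SAP 2.5). Multiplier 1300, with 95% two-sided chi-square limits (SAP 3.7.1).

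**Point estimate.** 1 / 2,015 × 1300 = 0.645. This rounds to the printed 0.6, so the estimate reproduces.

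**Interval by SAP 3.7.1.**

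- Lower: χ²(0.025; 2)/2 = 0.02532, and 0.02532 / 2,015 × 1300 = 0.016.
- Upper: χ²(0.975; 4)/2 = 5.5716, and 5.5716 / 2,015 × 1300 = 3.595.

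The result is (0.02, 3.6), or (0.0, 3.6) to one decimal. The printed pair is (0.1, 3.3).

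**Could a different number of cycles, or rounding, explain it?** With n = 1, the ratio of upper to lower limit is 5.5716 / 0.02532 = 220 whatever L is. After one-decimal rounding, the printed pair allows ratios from 3.25/0.15 = 22 to 3.35/0.05 = 67. Put in terms of cycles:

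- An upper limit between 3.25 and 3.35 needs L between 5.5716 × 1300 / 3.35 = 2,162 and 5.5716 × 1300 / 3.25 = 2,229.
- A lower limit of at least 0.05 needs L of at most 0.02532 × 1300 / 0.05 = 658.

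No L meets both conditions, so the pair cannot come from this formula.

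**Could another standard interval explain it?** At 2,015 cycles on the 13-cycle year (155 woman-years), per 100 woman-years:

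| Method | Lower | Upper |
|---|---|---|
| Clopper-Pearson, per cycle | 0.016 | 3.591 |
| Clopper-Pearson, per woman-year | 0.016 | 3.542 |
| Wilson score, per cycle | 0.114 | 3.648 |
| Wilson score, per woman-year | 0.114 | 3.564 |
| Wilson with continuity correction, per woman-year | 0.034 | 4.083 |
| Poisson score | 0.114 | 3.655 |
| Mid-P | 0.032 | 3.182 |
| Byar | 0.008 | 3.590 |
| Jeffreys | 0.070 | 3.016 |
| Log-normal (log-Wald) | 0.091 | 4.580 |
| 90% exact Poisson | 0.033 | 3.061 |

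Wald and Agresti-Coull give negative lower limits. None of these intervals rounds to (0.1, 3.3).

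**What does give (0.1, 3.3)?** Three routes do, each needing a score interval and a changed input:

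- Wilson on 2,015/12 = 167.9 woman-years, a 12-cycle year: 0.105 to 3.296.
- Wilson on 100/0.6 = 166.7 woman-years, taking the Pearl Index as exactly 0.6: 0.106 to 3.320.
- Wilson per cycle at 2,240 cycles, the all-ages goal in the Protocol synopsis: 0.102 to 3.282. The Poisson score interval there also matches, at 0.102 to 3.288.

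A 12-cycle year alone is not enough. The SAP formula with multiplier 1200 gives 0.015 to 3.318, which matches only the upper limit, and Wilson per cycle with 1200 gives 0.105 to 3.367. The documents do not show which route, if any, was used.

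**Size of the gap.** The upper limit is 3.595 against 3.3. Allowing for rounding, it is 3.595/3.35 = 1.07 to 3.595/3.25 = 1.11 times the printed value. For scale, the SAP formula at 2,015 cycles gives 0 to 2.38 with no pregnancies and 0.156 to 4.661 with two.

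**The case against.** The strongest reply is that SAP 3.7.1 defines the analysis interval, and section 2.5 does not say the planning figure used it. A planning interval may use another method. The printed figures are also not arbitrary: with 2,015 cycles counted at 12 per year, the Pearl Index is 0.596 and Wilson gives (0.105, 3.296), which rounds to all three printed values. The Protocol gives neither the 1300 multiplier nor an explicit 13-cycle year, so its statement could be called unexplained rather than wrong.

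Part of this stands. The cause cannot be established, and a 12-cycle Wilson interval is a plausible origin. It does not rescue the text. The SAP prints 13 cycles beside the interval, and the Protocol itself works in 28-day cycles (sections 12.4.1 and 20.7), which fits a 13-cycle year better than a 12-cycle one. Using 2,240 cycles would bring in women over 35, whom the primary analysis excludes, and neither document mentions a score interval. That several incompatible routes lead to the same pair is itself a reason to name the method.

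Two further points are fair. The printed interval is optimistic only at the upper end, since its lower limit of 0.1 is less favourable than 0.02. And limits of 3.3 and 3.6 support much the same reading of what one event can show.

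**Conclusion.** The printed interval is wrong as written. For one pregnancy in 2,015 cycles on the 13-cycle year, the SAP's method gives 0.645 with 95% CI (0.016, 3.595). The upper limit is understated by about 0.3 per 100 woman-years (7% to 11%), and the lower limit is overstated by less than 0.1. That the pair cannot come from SAP 3.7.1 rests only on the formula and the printed limits. That it comes from no other method at these inputs rests on the intervals tried above.

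The consequence is minor. No success criterion or formal sample size depends on the interval. SAP 3.1.2 also records that "The analysis of 1-year data was the main analysis for the study" and that it had already been done. The CI for the observed Pearl Index follows the explicit formula in 3.7.1, so no result changes.

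**What to change.** In SAP 2.5 and the Sample Size part of the Protocol synopsis, replace the interval with text such as: *One pregnancy in 2,015 evaluable cycles gives a Pearl Index of 0.65 with an exact Poisson 95% CI of (0.02, 3.6), calculated as in SAP 3.7.1.* Two decimals on the lower limit avoid printing it as 0.0.

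If a different planning method was intended, name it and print the limits it gives at 2,015 cycles on the 13-cycle year; Wilson per cycle, for example, gives (0.11, 3.65). Because the 1-year analysis has been done, mark the change as a correction to a planning figure.

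The cost is a text edit in two places, and the stated precision becomes slightly less favourable at the upper limit. Data, analyses and study conduct are unaffected.
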